## 5.9 RESPONSE CRITERIA

- 5.9.1** The definition of local recurrence is histologic evidence of recurrent carcinoma, either invasive or non-invasive in the nipple-areola complex in the ipsilateral breast.
- 5.9.2** Clinical evidence of carcinoma by physical exam and/or mammograms/MRI will not be evidence of local recurrence until biopsy proof.
- 5.9.3** **Overall survival time** is defined from the date of surgery until the date of death due to any cause. In the absence of death, follow-up time will be censored by the date of last contact.
- 5.9.4** **Disease-free survival time** is defined from the date of surgery until the date of documented recurrence (local or distant) or breast cancer-related death, whichever occurs first. Patients who die without documentation of recurrence will be considered to have had disease recurrence at the time of death, unless there is documented evidence that no recurrence occurred before death. In other words, 'unknown cause of death' will be considered an event for the disease-free survival analysis. In the absence of any event defining disease recurrence, follow-up time will be censored at the date of last documented recurrence-free status.

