## 4.2 Radiation Therapy

### 4.2.1 Dose levels and schedule

Dose levels †	Description
Dose Level I = 20 Gy	10 fractions of 2.0 Gy
Dose Level II = 25 Gy (starting dose)	10 fractions of 2.5 Gy
Dose Level III = 30 Gy	10 fractions of 3 Gy
Dose Level IV = 35 Gy	10 fractions of 3.5 Gy

† Treatment will be delivered twice a day, minimum of 4 hours apart, **for 5 days**, preferable in consecutive working days.

**4.2.2 Treatment Planning and Imaging:** Treatment planning and delivery should be performed with the patient in supine position, on a breast board. A treatment planning CT scan will be required to define the clinical target volume (CTV) which will include the nipple-areola complex. At the time of CT Simulation, the NAC will be marked on the skin, to be seen on the CT images for planning. A second simple simulation might be performed to verify treatment parameters and treatment field on the patient, according to plan.

**4.2.3 Beam Angles/Treatment Position:** The patient will be treated in supine position, with electrons. The energy of the electrons assigned for treatment will be dependent on the plan to cover the area of NAC appropriately, as per radiation oncologist's discretion.

**4.2.4 External Beam Equipment:** Megavoltage equipment is required with a range of electrons energy.

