## 5.8 Patient follow-up

- 5.8.1** Vital status
- 5.8.2** Disease status, classified local, regional, or distant
- 5.8.3** Site(s) and date of first failure in each category above
- 5.8.4** Relationship of the recurrence to the irradiated volume
- 5.8.5** Cosmetic evaluation by patient and physicians
- 5.8.6** Effects of treatment
- 5.8.7** Follow-up physical examination
- 5.8.8** Photographs will be taken at the discretion of the P.I. and Sub-P.I.
- 5.8.9** AE and Concomitant Medication reporting from post-operative visit up to 30 days post radiation treatment.

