## 10.2 Planned Analysis

**Patient demographics** (age, race/ethnicity), **laboratory parameters, disease characteristics** (such as, tumor stage, grade), will be summarized using descriptive statistics: counts and percentages, range, median, mean, and standard deviation, as appropriate [23].

**Toxicities** resulting from radiation treatment will be tabulated by type, grade, duration, and attribution to treatment according to NCI CTCAE version 3.0, and by administered NAC radiation dose. A patient-level summary by worst grade toxicity will be included. Any grade 3, 4 or 5 or unexpected lower grade toxicities will be reported.

**Intraoperative parameters and perioperative parameters** (complications, events, and findings) will be described in the operative report as routinely done.

**Surgery success rate**, defined as the proportion of patients who had successful NAC sparing surgery with reconstruction divided by the total number of study patients, will be determined.

**Cosmetic results** will be assessed by both the physician(s) and the patients at 3, 6 and 12 months, using a 4-category ordinal scale (excellent, good, fair, and poor). Data will be summarized in terms of number and % of patients in these 4 possible categories at those assessment times separately for assessment by physician and by patient. Statistical analysis methods for contingency tables will be used to compare changes over time for each evaluator (physician or patient), and also to compare agreement between physician and patient assessment at a given time. [24]

To gather data on recurrence and survival, all patients will be under follow-up for a minimum of 5 years, unless they withdraw consent or die within that time.

Given the small study size and the expected low incidence of recurrence, we do not expect any such recurrences within 5 years. However, if patients do recur, the **number of recurrences** will be reported, along with corresponding summary regarding time to recurrence, type of recurrence -- local (ipsilateral nipple-areola recurrence in-field, peripheral, or extra-field location) or distant, irradiated volume, and radiation dose. If the number of events allows, **disease-free survival and overall survival** will be estimated by the Kaplan-Meier method. [25]

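### Disease-free survival as written censors a patient whose only failure is regional; separately, Section 10.2 names no comparison of cosmesis with the pre-radiation rating

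*Combined protocol and SAP*

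**What the plan says.** All references are to the combined protocol and SAP.

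**Disease-free survival.** Section 5.9.4 says that DFS "is defined from the date of surgery until the date of documented recurrence (local or distant) or breast cancer-related death". Its last sentence reads: "In the absence of any event defining disease recurrence, follow-up time will be censored at the date of last documented recurrence-free status". Section 5.9.1 fixes what local means: "The definition of local recurrence is histologic evidence of recurrent carcinoma, either invasive or non-invasive in the nipple-areola complex in the ipsilateral breast". Section 5.9.2 adds that clinical or imaging signs do not count as local recurrence until a biopsy confirms them.

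The data collection is wider than the endpoint. Section 5.8.2 records "Disease status, classified local, regional, or distant", Section 5.8.3 records "Site(s) and date of first failure in each category above", and Section 5.8.4 records "Relationship of the recurrence to the irradiated volume".

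Section 10.2 describes the type of recurrence to be reported as "local (ipsilateral nipple-areola recurrence in-field, peripheral, or extra-field location) or distant". It expects no recurrences within 5 years and plans Kaplan-Meier estimates only when there are enough events.

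**Cosmesis.** Section 5.10.1 has patient and physician grade cosmesis before radiation, a rating it labels baseline, and at 1, 3, 6 and 12 months after radiation. Appendix I marks the same five occasions. Section 10.2 names 3, 6 and 12 months, tabulates the categories at those times, and plans contingency-table methods for change over time by evaluator. It does not mention the baseline or 1-month rating.

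**The concern.** The follow-up forms recognise three classes of failure, but the DFS definition counts two. The class left out is not absorbed by the others, because local is defined narrowly and regional is listed apart from distant. A patient with a documented regional failure would then leave the risk set at her last recurrence-free date, and leave it because she failed. Censoring of that kind is informative and can only make DFS look better. Survival and recurrence are a stated secondary objective (Section 2.2), so the description of outcome would omit a failure that the trial had recorded.

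The background shows that failure outside the NAC is a realistic pattern. Section 1.2 reports that the single local recurrence in the study of nipple-sparing mastectomy with intra-operative NAC irradiation lay in the clavicular region, away from the NAC. Under Section 5.9.1 it would not be local here. Unless it were classed as distant, it would not be a DFS event.

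For cosmesis, Section 6.2.1 warns that the irradiation might change the cosmetic result. The natural comparison is before against after radiation, and Section 10.2 does not specify it.

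**Working it through.** The plan gives no event count, power or precision for DFS or cosmesis, so there is no stated figure to reproduce. The check compares the passages and then adds an illustration of size.

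**Step 1: class of first failure against the DFS rule**

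| Only failure | Collected (5.8.2, 5.8.3) | Local under 5.9.1 | DFS event under 5.9.4 | Class in 10.2 summary |
|---|---|---|---|---|
| Ipsilateral NAC, biopsy-proven | yes | yes | yes | local |
| Regional | yes | no | no, censored | none |
| Ipsilateral chest wall or skin outside the NAC | yes | no, read literally | no, read literally | unclear |
| Distant | yes | no | yes | distant |

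The regional row is unambiguous. The chest-wall row is less so. In Section 10.2 the extra-field wording qualifies nipple-areola recurrence, which points to the NAC only. But Section 4.2.2 says "A treatment planning CT scan will be required to define the clinical target volume (CTV) which will include the nipple-areola complex", so a recurrence outside the irradiated field may well lie outside the NAC. The extra-field label may be meant to reach such recurrences, which Section 5.9.1 excludes.

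**Step 2: size, if Kaplan-Meier is run**

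Inputs: 12 to 18 patients in dose finding plus 12 in the expansion cohort (Section 10.1), so n = 24 to 30. Assumptions: all n patients are in the DFS analysis, *k* of them have a regional-only failure at month 24, and all others are event-free with complete 5-year follow-up.

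- As written there are no events, so S(60) = 1.000 for any *k*.
- With the failures counted, S(60) = 1 − k/n.
- k = 1: 1 − 1/24 = 0.958; 1 − 1/30 = 0.967.
- k = 3: 1 − 3/24 = 0.875; 1 − 3/30 = 0.900.

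Now add one NAC or distant event in another patient at month 36, with k = 1:

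- As written the censored patient has left the risk set: 1 − 1/23 = 0.957 (n = 24); 1 − 1/29 = 0.966 (n = 30).
- Counted: (1 − 1/24)(1 − 1/23) = 22/24 = 0.917; (1 − 1/30)(1 − 1/29) = 28/30 = 0.933.

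**Step 3: what happens if the same patient later has a counted event**

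Suppose the patient with regional failure at month 24 has a distant recurrence at month 48, remains under follow-up, and is the only patient to fail. As written, S(36) = 1.000 and S(60) = 0.958 or 0.967. Counted from the regional failure, S(36) = S(60) = 0.958 or 0.967. The two definitions then differ only between months 24 and 48.

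This depends on the month-48 event being captured, and the documents do not settle that. Section 10.2 promises at least 5 years of follow-up. Section 8.1.1 lists disease progression among the reasons to discontinue a patient from the study. Section 10.1 ties follow-up for recurrence and survival to clinic visits made on clinical grounds, and Appendices I and IV leave years 2 to 5 to the investigator's discretion.

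**Step 4: cosmesis**

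Five rating times are collected and three are named in Section 10.2; the two not named are baseline and 1 month. Four later times and two raters give 4 × 2 = 8 possible paired changes from baseline, and Section 10.2 names none of them. If the analysis uses only the three named times, a drop between baseline and 3 months that then stays stable shows no change.

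**The case against.** **The effect may never be visible.** With no recurrences expected and Kaplan-Meier conditional on events, a curve with zero or one event would probably not be drawn. The default output is a count with time and type. This stands as a limit on size. It does not remove the gap, because the type list in Section 10.2 has no regional class either.

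**Local or distant may be shorthand for any recurrence.** That may be what was meant. But Section 5.8.2 lists regional separately and Section 5.9.1 defines local narrowly, so the shorthand reading overrides two other passages.

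**Stronger readings to avoid.**

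- A reader might infer that every ipsilateral failure outside the NAC is certainly excluded. The literal wording says so, but the extra-field phrase in Section 10.2 leaves the intent open.
- A reader might infer that a later distant recurrence or breast-cancer death always rescues the event, so that it is only counted late. The opposite inference is that the failure is always lost. The follow-up passages conflict, so neither is secured.
- A reader might infer that Section 10.2 rules out a comparison with baseline. It does not. The sentence on change over time lists no times; the restriction is inferred from the two sentences before it, and Section 5.10.1 calls the pre-radiation rating baseline. The fair statement is that the comparison is not specified.

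**Conclusion.** The DFS definition is wrong as written for regional-only failure: following it censors a patient whom the trial has recorded as having failed. For ipsilateral failure outside the NAC, Sections 5.9.1 and 10.2 do not agree clearly and must be reconciled. The cosmesis point is a free improvement, not an error.

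The impact is small. DFS is secondary and descriptive, and the 100% against 95.8% or 96.7% contrast rests on an assumed single failure, otherwise complete 5-year follow-up, and a Kaplan-Meier estimate that might not be made. The documents do not support any inference that the recommended phase II dose, the dose-limiting toxicity rules, the sample size or the stopping guidelines are affected. The reason to act is that the event definition is best settled before any recurrence has to be classified.

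**What to change.** **Section 5.9.** Define a DFS event as any ipsilateral breast or chest-wall, regional or distant recurrence, or breast cancer-related death. Keep the existing rule for deaths of unknown cause. State the documentation standard for the added events next to Section 5.9.2, which now covers local recurrence only. Keep NAC recurrence as a separately reported outcome, because the stated hypothesis concerns local control in the NAC.

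**Section 10.2, recurrence.** Add regional and non-NAC local classes to the summary, and say what extra-field covers. Reconcile the follow-up statements in Sections 8.1.1, 10.1 and 10.2 and Appendices I and IV, so that it is clear whether a patient with a first failure is still followed for recurrence and survival.

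**Section 10.2, cosmesis.** Add the baseline and 1-month ratings and analyse paired change from baseline, separately for patient and physician. State that, without an unirradiated arm, this change does not isolate the effect of radiation.

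**Cost.** Wording only. Regional status, site and date of first failure, relation to the irradiated volume, and the baseline and 1-month cosmesis ratings are already collected. No patients or visits are added.

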## 5.10 DEFINITIONS OF LEVELS OF COSMETIC OUTCOME (07-15-2011)

**5.10.1** Cosmesis will be graded by the patient and by the radiation oncologist or the surgeon prior to radiation (baseline), and 1, 3, 6 and 12 months after completion of radiation therapy as follows: Plus or minus 2 weeks.

**Excellent:** when compared to the untreated breast, there is minimal or no difference in the sizes, shape or texture of the treated breast. There may be mild thickening or scar tissue of the reconstructed breast or skin, but not enough to change the appearance.

**Good:** there is mild asymmetry in the size or shape of the treated reconstructed breast as compared to the normal breast. The thickening or scar tissue within the breast causes only mild change in the shape.

**Fair:** there is obvious difference in the size or shape of the reconstructed breast. This change involves  $\frac{1}{4}$  or less of the breast.

**Poor:** marked change in the appearance of the treated breast involving more than  $\frac{1}{4}$  of the breast tissue.

**Clarification:** (Evaluation of the treated nipple-areola complex)

**Color: Natural Score 0 or 1**

**Shape: Round Score 0 or 1**

**Nipple: Central Score 0 or 1**

**Nipple: Everted Score 0 or 1 Total Score Report:**

**4 =excellent**

**3= good**

**2 = fair**

**1=poor**

## 6.0 TOXICITIES AND COMPLICATIONS

### 6.1 Surgery

#### 6.1.1 General risks of Surgery

The general risks of surgery include anesthetic risk, bleeding, infection, pulmonary and cardiac complications and death. These general risks will be explained in detail to the patient and a separate standard surgical consent form will be completed prior to enrollment.

### **6.1.2 Specific risks of NAC-sparing Mastectomy**

The operative procedure is performed under general anesthesia and following standard breast cancer operation. The NAC sparing during mastectomy will add a frozen biopsy of the tissue underneath the NAC is expected to prolong the anesthesia for approximately ½ hour. A small risk of NAC necrosis postoperative exists due to possibility of decrease in vascularization.

### **6.2 General risks of Breast Reconstruction with Implants or Autologous Tissue.**

The general risks of plastic surgery reconstruction include anesthetic risk, bleeding, infection, loss of the reconstructed breast with autologous tissue secondary to necrosis, capsulitis of the breast implant, cardiac and pulmonary complications and death.

#### **6.2.1 Specific risks of NAC-sparing Mastectomy with Immediate Reconstruction with Implants or Autologous Tissue followed by prophylactic NAC Irradiation**

Besides the general risks of mastectomy and plastic reconstructive surgery with implants or autologous tissue, postoperative prophylactic NAC Irradiation will give a small increased risk of NAC necrosis, which in some cases will resolve spontaneously or in some cases will require a second operation. The aesthetic result of NAC-sparing Mastectomy with Immediate Reconstruction with Implant or Autologous Tissue followed by Prophylactic NAC Irradiation might alter the cosmetic results secondary to skin fibrosis or discoloration.

### **6.3 General risks of Radiation**

Fatigue is anticipated systemic reaction to radiation treatment. Skin erythema, hyperpigmentation and desquamation (dry or moist) may also occur, and they are usually temporary. Edema and tenderness are possible side effects of treatment. There is a rare possibility of development of secondary malignancy.

#### **6.3.1 Specific risks of Prophylactic NAC Irradiation after NAC-sparing Mastectomy and Reconstruction.**

The addition of Prophylactic NAC irradiation after NAC-sparing Mastectomy and Reconstruction include necrosis of NAC, with a need for additional surgical procedure for repair; delayed wound healing, poor cosmesis secondary to permanent hypopigmentation or hyperpigmentation of the skin of the NAC or skin fibrosis.

## 7.0 Adverse Event Reporting

The descriptions and grading scales found in the revised NCI Common Terminology Criteria for Adverse Events (CTCAE) version 3.0 will be utilized for adverse event reporting. A copy of the CTCAE version 3.0 can be downloaded from the CTEP web site (<http://ctep.cancer.gov/reporting/ctc.html>).

### 7.1 Definitions:

7.1.1 **Adverse events** (AE's) will use the descriptions and grading scales found in the NCI Common Toxicity Criteria in Appendix II.

**Adverse events:** Any unfavorable and unintended sign (including abnormal laboratory finding), symptom, or disease temporally associated with the use of a medical treatment or procedure, regardless of whether it is considered related to the treatment or procedures; also and “unanticipated problem” of any nature (e.g., psychological or social harm)

7.1.2 A **serious adverse event** (experience) or reaction is any untoward medical occurrence that at any dose: results in death, is life-threatening, requires inpatient hospitalization or prolongation of existing hospitalization, results in persistent or significant disability/incapacity, or is a congenital anomaly/birth defect.

The definition of serious adverse event (experience) also includes **important medical events**. Medical and scientific judgment should be exercised in deciding whether reporting is appropriate in other situations, such as important medical events that may not be immediately life-threatening or result in death or hospitalization but may jeopardize the patient or **may require intervention** to prevent one of the other outcomes listed in the definition above. These should also usually be considered serious. Examples of such events are intensive treatment in an emergency room or at home for allergic bronchospasm; blood dyscrasias or convulsions that do not result in hospitalization; or development of drug dependency or drug abuse.

7.1.3 **Expected events** are those that have been previously identified as resulting from administration of the treatment.

7.1.4 An adverse event is considered **unexpected** when either the type of event or the severity of the event is *not* listed in: the current NCI Agent-Specific Adverse Event List; the investigator's brochure or the information section of this protocol.

7.1.5 The definition of **related** is that there is a reasonable possibility that the drug caused the adverse experience.

## 7.2 Purpose

Adverse event data collection and reporting, which are required as part of every clinical trial, are done to ensure the safety of patients enrolled in the studies as well as those who will enroll in future studies using similar agents. Note: Chemotherapy **related** adverse event reporting will not be performed for patients receiving standard of care chemotherapy in the follow-up period starting 2 weeks post radiation. Adverse events are reported in a routine manner at scheduled times during a trial (please follow directions for routine reporting provided in the Data Reporting Section). The following sections provide information about reporting.

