#### **4.2.6 Definition of dose limiting toxicity (DLT)**

Dose limiting toxicity (DLT) is defined as any of the following toxicities occurring during radiation treatment period plus an **additional observation period of 30 days** following completion of NAC radiation:

- a) Grade 4 skin rash
- b) Grade 4 pain
- c) NAC necrosis
- d) Any toxicity requiring interruption of the NAC irradiation by > 2 weeks (14 calendar days), except if interruption is secondary to LINAC machine or unpredictable weather problems or unrelated medical conditions that would prevent the subject to come for treatment.
- e) Any grade 4 or 5 treatment-related toxicity

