### **4.3 Chemotherapy**

**4.3.1** Chemotherapy, if indicated by oncologist, will be delivered at least 2 weeks from the last radiation treatment.

**4.3.2** The type of chemotherapy will be at discretion of the oncologist physician.

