## 10.0 STATISTICAL CONSIDERATIONS

### 10.1 Study Size

For the purpose of dose escalation of NAC-radiation treatment, **evaluable patients** will be defined as any eligible patient that begins NAC irradiation treatment. However to evaluate feasibility of the NAC-sparing mastectomy with reconstruction, any patient who undergo surgery will be considered evaluable.

Following the dose escalation/de-escalation procedure described in section 4.2, we anticipate that 12 to 18 evaluable patients will be enrolled in this phase I study *during the dose-finding part*. The **number of evaluable patients** that will be needed depends on the number of times the NAC-radiation dose is escalated or possibly de-escalated. If the escalation occurs from dose level II up to dose level IV, between 14-18 evaluable patients will be required. If the dose is de-escalated after dose level II been evaluated in 6 patients, then 12 evaluable patients will be required, assuming 6 patients would be evaluated at dose level I. With 6 evaluable patients, the probability of not escalating when the true DLT rate is 35% is 68%. If the true DLT rate is 20%, the probability that the dose will be escalated is 66%.

A maximum of 6 patients per year is expected to be enrolled, since each patient must be evaluated for a minimum of 35 days and at most two patients will be enrolled simultaneously (within < 30 days after completion of the 5 days NAC radiation treatment). Thus, the expected accrual period is between 2-3 years.

An **additional expansion cohort of 12 patients** will be enrolled at the “**potential**” **recommended phase II dose (RP2D)** over an expected accrual period of 2 years.

To gather data on recurrence and survival, all patients will be followed at their clinic visits as clinically indicated.

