## **10.3 Interim Monitoring**

### **10.3.1 Role of the Research Team and the DSMC**

The Research Team will continuously monitor study accruals and adverse events from both surgery and radiation treatment. In particular, for the purpose of escalation and de-escalation (section 4.2) patients will be monitored closely during the 30 days after completion of NAC radiation treatment, and subsequently for any toxicity or adverse reaction to treatment. All toxicities, regardless their grade, will be recorded in the patient case report form using NCI/CTEP Common Terminology Criteria for Adverse Events (CTCAE) version 3.0.

The Sylvester Comprehensive Cancer Center's Data and Safety Monitoring Committee (DSMC) will monitor this protocol according to the Cancer Center's DSM Plan. In its oversight capacity, the DSMC bears responsibility for suspending or terminating this study.

DSMC oversight of the conduct of this trial includes ongoing review of accrual and adverse event data. The guidelines appearing in Sections 10.3.2, and 10.3.3 are offered for DSMC consideration in assessing accrual, adverse events. In addition, the DSMC will review reports from all audits, site visits, or study reviews pertaining to this clinical trial and take appropriate action.

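### Section 7.2 waives reporting of chemotherapy-related adverse events from 2 weeks after irradiation, inside the 30-day DLT window, and no rule says how mixed-cause events count

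*Combined protocol and SAP*

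**What the plan says.** All references are to the combined protocol and SAP.

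- **DLT window.** Section 4.2.6 covers the irradiation period and the 30 days "following completion of NAC radiation". Section 10.1 adds that "each patient must be evaluated for a minimum of 35 days".
- **DLT items.** Items (a) to (c) of 4.2.6 are grade 4 rash, grade 4 pain and NAC necrosis, with no condition on cause. Item (e) covers grade 4 or 5 toxicity related to treatment, without saying which treatment.
- **Chemotherapy.** Section 4.3.1 says that chemotherapy, if indicated, "will be delivered at least 2 weeks from the last radiation treatment". The treatment plan table in section 4.0 lists it alongside surgery and irradiation.
- **The waiver.** Section 7.2 has a note confined to events related to chemotherapy. For those, "adverse event reporting will not be performed for patients receiving standard of care chemotherapy in the follow-up period starting 2 weeks post radiation".
- **Recording elsewhere.** Section 5.8.9 asks for "AE and Concomitant Medication reporting from post-operative visit up to 30 days post radiation treatment". Section 10.3.1, on monitoring for escalation, says "All toxicities, regardless their grade, will be recorded in the patient case report form". Neither makes an exception for chemotherapy.
- **Attribution.** Section 7.1.5 treats an event as related if "there is a reasonable possibility that the drug caused the adverse experience". Section 7.2.2 gives five attribution categories, judged against protocol therapy. No section covers an event that radiation and chemotherapy could both have caused.
- **Visit.** Appendix I schedules one adverse event evaluation after irradiation, at 1 month, give or take 1 week.

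**The concern.** The waiver switches on at about the time chemotherapy may start, while the DLT window still has just over half of its post-radiation part to run. The bar for calling an event related is low. Suppose NAC necrosis appears on day 22 in a patient who began chemotherapy on day 14. If chemotherapy is a reasonable possibility, 7.2 says the event is not reported. Under 4.2.6 (c) the same event is a DLT whatever its cause. The site cannot follow 7.2 and also follow 5.8.9 and 10.3.1.

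The DLT count is the only input to escalation and to the MTD, which becomes the potential RP2D and so serves the primary objective. The rule turns on a single event: 1 of 6 escalates and 2 of 6 does not. A gap in how events are recorded and attributed therefore bears directly on the main result, even if it touches few patients.

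**Working it through.** **Overlap.** Count days from the last irradiation. The window closes at day 30 and chemotherapy may start at 2 weeks (day 14). The overlap is 30 − 14 = 16 days (days 15 to 30), which is 16/30 = 53% of the post-radiation window, or 16/35 = 46% of the 35-day evaluation period (5 days of irradiation plus 30).

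**The same event under each section.** Take NAC necrosis, or grade 4 rash or pain, between days 15 and 30 in a patient on chemotherapy, where chemotherapy is a reasonable possible cause:

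| Section | Result |
|---|---|
| 4.2.6 (a)–(c) | DLT, no condition on cause |
| 5.8.9 | Reported, to 30 days |
| 10.3.1 | Recorded, any grade |
| 7.2 | Not reported |

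Now take a grade 4 toxicity due only to chemotherapy. Under 4.2.6 (e) it is a DLT if treatment includes chemotherapy, and not if treatment means irradiation alone. The text does not say. Under-counting and over-counting are both possible.

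**The plan's own figures (section 10.1).** Six patients per level; escalate on 0 or 1 DLT. With DLT rate p,

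P(escalate) = (1 − p)^6 + 6p(1 − p)^5.

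- p = 0.35: 0.075 + 0.244 = 0.319, so P(not escalate) = 0.681. The plan states 68%.
- p = 0.20: 0.262 + 0.393 = 0.655. The plan states 66%.

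Both reproduce.

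**Illustration of under-counting.** Let m be the share of true DLTs left uncounted, so the counted rate is q = p(1 − m). The documents give no value for m; the values below are assumptions. At p = 0.35:

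| m (assumed) | q | P(escalate) | P(not escalate) |
|---|---|---|---|
| 0% | 0.350 | 0.075 + 0.244 = 31.9% | 68.1% |
| 4% | 0.336 | 0.086 + 0.260 = 34.6% | 65.4% |
| 10% | 0.315 | 0.103 + 0.285 = 38.8% | 61.2% |
| 20% | 0.280 | 0.139 + 0.325 = 46.4% | 53.6% |

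**What m is made of.** It is the product of three unknowns: the share of patients starting chemotherapy before day 30, the share of DLTs falling in days 15 to 30, and the share of those left out as chemotherapy events. If DLTs were spread evenly over the 30 days, the second factor would be 53%. Then 30% × 53% × 25% = 4%. Reaching m = 20% would need 0.20/0.533 = 37.5% of all late DLTs to be lost. None of these inputs is in the documents.

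**Visit timing.** Taking 1 month as 30 days, the visit may fall as early as day 30 − 7 = 23, about a week before the window closes. That does not match the 35-day minimum evaluation.

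**The case against.** The best defence is that DLT counting is governed by 4.2.5 and 4.2.6, not by 7.2. Items (a) to (c) ignore cause, and 10.3.1 requires close monitoring for 30 days and recording of every toxicity. Sections 7.3.1 and 7.3.2.1 separately send serious events to the investigator and the IRB. On this view a DLT is lost only if a site lets the 7.2 note override the rest. Two weeks is also only a minimum, chemotherapy is given only if indicated, and in-situ disease is eligible, so few patients may be affected.

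This limits the reach of the problem but does not remove it. The 7.2 note is a specific exception to general statements, and a site could reasonably apply it as written. Serious-event reporting is not a full safety net: item (c) sets no grade, so not every NAC necrosis need be serious.

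Several stronger readings are tempting, and the documents do not support them:

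- *All related events are waived.* The note is limited to chemotherapy-related events; radiation-related events stay reportable throughout.
- *Chemotherapy patients are observed for only half the window.* They keep the 1-month visit, the 30-day monitoring and the 35-day minimum.
- *The error can only favour escalation.* Items (b) and (e) could also count a chemotherapy toxicity, which works against escalation.
- *The expansion-cohort guideline loses the same events.* Section 10.3.2 already counts toxicity with a possible radiation cause, so its standard takes in mixed-cause events.
- *A particular inflation of the escalation probability is established.* It is not; the uncounted share is assumed.

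**Conclusion.** The point holds as a contradiction between sections of the plan and as a missing rule. From day 15 to day 30, section 7.2 conflicts with 5.8.9 and 10.3.1. If 7.2 is followed, an event that 4.2.6 (a) to (c) makes a DLT can stay out of the six-patient count. Item (e) leaves open the opposite error. The DLT endpoint is therefore not fully defined for patients who start chemotherapy before day 30, and it is unaffected by this point in everyone else.

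The net direction and size cannot be worked out, because the documents give neither the share starting chemotherapy early nor the timing and attribution of DLTs. The illustrated rise from 32% to between 35% and 46% rests on an assumed 4% to 20% of DLTs uncounted, no offsetting over-count, and a true rate of 35%. It shows that a one-event rule is sensitive to small losses; it does not estimate what will happen. The case for correcting the text is that it concerns the primary endpoint and the correction is cheap.

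**What to change.** 1. Amend the note in 7.2 so that the waiver of chemotherapy-related reporting begins only after the 30-day DLT window closes. Through day 30, record every event whatever its attribution, as 5.8.9 and 10.3.1 already require.
2. Reconcile 4.2.6, 4.3.1, 5.8.9, 7.2 and 10.3.1 so that one stated rule governs how events possibly due to both radiation and chemotherapy count as DLTs, and state which treatment item (e) means. The choice is the sponsor's. Requiring a radiation attribution for every item would narrow (a) to (c), which now count whatever the cause, so that should not happen by default.
3. Reconcile the 1-month visit in Appendix I with the 30-day window and the 35-day minimum by confirming DLT status at or after day 30.
4. Tabulate DLTs by whether chemotherapy had started before day 30.

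The timing of chemotherapy is not changed. The cost is a short amendment and about two more weeks of adverse event recording in patients on chemotherapy. The downside is that some events caused by chemotherapy may enter DLT review.
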